8.5.2 Treatment Compliance

Treatment Compliance will be derived using the formula below:

 $\frac{(Total No. of capsules dispensed - Total No. of capsules returned) \times 50}{Total assigned dose} \times 100$

Where total assigned dose (in mg) will be derived by sum of (AM+PM dose) \times duration of this dose level for all different dosing levels.

Study drug compliance will be summarized using standard summary statistics based on safety population. Study drug compliance will also be summarized in "<80%", 80% - 120%" and ">120%" using frequency tables.

A complete listing of drug accountability will be presented based for the safety population.

8.5.3 Drug Tolerability and Modifications

Summary of subjects with intolerable doses and dose modifications will be presented using frequency and percentages for each visit based on safety population.

A complete listing of drug tolerability/modification by visits will be presented based for the safety population.

8.6 Safety Analyses

Safety assessments will be conducted throughout the entire study period. Analyses will be performed using the safety population, unless otherwise specified. All safety data will be summarized by period. No formal statistical hypothesis testing will be conducted.

The safety evaluations will include primary hepatic and secondary hepatic safety analysis. Analyses of adverse events, clinical laboratory tests (clinical chemistry/serology, hematology, urinalysis, other tests, additional liver testing & other testing), vital signs, physical examination, 12-lead electrocardiogram (ECG) and serum/urine pregnancy results will also be presented. The safety analyses involving changes from baseline to a specific time point in safety variables (e.g., laboratory parameters, vital signs, and ECG) will only include subjects from the safety population who have data available for both the baseline and the time point under consideration unless otherwise specified.

8.6.1 Analysis of Primary Safety Endpoint

Descriptive statistics (n and percentage) along with exact binomial 95% Confidence Interval (CI)) will be presented to summarize the proportion of subjects who develop ALT levels >3 x ULN that were assessed by the independent HERC to be related to lixivaptan and resulted in discontinuation of the study drug during the Titration and Maintenance Periods.

The above summary will be presented additionally based on the investigator decision alone as documented in the CRF.

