
Statistical Methods:
	
Sample Size: Up to 50 subjects will be enrolled and treated based on the design of a similar study with a different drug.
 
Populations for Analysis: The Enrolled Population is defined as all subjects who meet inclusion/exclusion criteria during Screening Period and complete Visit 3. All general summaries, except safety and efficacy analyses are based on the Enrolled Population, unless specified otherwise. The Safety Population is a subset of the Enrolled Population defined as those subjects who received at least 1 dose of lixivaptan. This population will be utilized for all safety analyses. The Efficacy Population is a subset of the Safety Population defined as those subjects who have at least 1 eGFR determination during the Baseline Period and have at least 1 eGFR determination during the Follow-up Period. This population will be used for all efficacy analyses. The Pharmacokinetic (PK) Population is a subset of the Safety Population defined as those subjects who had at least 1 on-therapy evaluable PK measurement. The Pharmacodynamic (PD) Population is a subset of the Enrolled Population defined as those subjects who have at least 1 set of urine specific gravity and urine osmolality measurements from the same specimen.
 
Analysis of Primary and Secondary Safety Endpoint: Descriptive statistics (n and percentage) and 95% confidence intervals will be used to present the proportion of subjects who develop ALT levels >3 x ULN that were assessed by the independent HERC to be at least highly likely related to lixivaptan and resulted in discontinuation of the study drug during the Titration or Maintenance Periods. Similarly, descriptive statistics and 95% confidence intervals will be utilized to present the 2 secondary endpoints: the proportion of subjects who develop ALT levels >5 x ULN during the Titration or Maintenance Periods that were assessed by the independent HERC to be related to lixivaptan and resulted in discontinuation of the study drug and the proportion of subjects who develop ALT levels >3 x

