	
ULN during the Titration or Maintenance Periods that were assessed by the independent HERC to be related to lixivaptan and resulted in lixivaptan dose reduction.
 
Analysis of Additional Hepatic Safety Endpoints:
 
Proportion of subjects who develop during the Titration and Maintenance Periods:
 
 • >3 x, 5 x, 10 x, and 20 x ULN elevations for ALT • >3 x, 5 x, 10 x, and 20 x ULN elevations for AST • >3 x, 5 x, 10 x, and 20 x ULN elevations for either ALT or AST • ALT or AST levels >2 x their baseline • Any elevation of total bilirubin to >2 x ULN • Any elevation of alkaline phosphatase (ALP) >2 x ULN • Elevation of aminotransferase (>3 x ULN) accompanied by elevated bilirubin (>2 x ULN) and displayed as evaluation of Drug-Induced Serious Hepatotoxicity (eDISH) plots • Elevation of aminotransferase in temporal association with nausea, vomiting, anorexia, abdominal pain, or fatigue • Possible liver-related deaths and liver-related treatment discontinuations. 
Analysis of Additional Non-hepatic Safety Endpoints:
 
The following safety variables will be summarized using appropriate descriptive statistics:
 
Treatment-emergent adverse events, clinical laboratory data, 12-lead ECGs, and vital signs. Potentially clinically significant results in certain clinical laboratory tests, 12-lead ECGs, and vital signs identified using prospectively defined criteria will also be summarized descriptively.
 
Efficacy Analysis:
 
Baseline eGFR is defined as the mean of the 3 eGFR assessments obtained during the Baseline Period. The endpoint eGFR is defined as the mean of 3 eGFR assessments obtained during the Follow-up Period. Descriptive statistics (n, mean, standard deviation, median, minimum, and maximum) will be presented for the change from baseline in eGFR at endpoint.

--	--

Figure 1. Study Schematic

Table 1 Schedule of Procedures

Assessment	Screening (1-8 weeks)		Baseline (Weekly \pm 3 days) (3 weeks)	Titration Period (Weekly \pm 3 days) (Up to 6 weeks)						Maintenance Period (every 28 days \pm 3 days) for 52 weeks		Follow-up Period (4 weeks after last dose ^b)
	V1	V2 ^a		V3, 4, 5	V6	V7	V8	V9	V10	V11	V12-V23	
Visit Number	V1	V2 ^a	V3, 4, 5	V6	V7	V8	V9	V10	V11	V12-V23	V24	V25, 26, 27
Informed consent	X											
Demographic information	X											
Medical history/Prior meds	X	X										
Review eligibility (Inclusion/Exclusion)	X	X	V5									
ECG	X		V5							V17	X	V27

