7.3.7.3 Special Reporting of Liver Events

A liver dysfunction details eCRF will be utilized during the study. The type of information needed to complete it is provided in Appendix 4 ([Section 13.4](#)). The purpose of the liver dysfunction details eCRF and additional testing is to facilitate review of each subject who develops liver chemistry test abnormalities and/or signs or symptoms of liver dysfunction during the study to determine the probable cause(s) of these abnormalities. The review will be performed by an independent HERC using DILIN probability criteria, modified (0 to 5% = unrelated; 6 to 25% = unlikely, 25% to 50% = possibly, 51% to 75% = probably, 76% to 95% = very likely, >95% = definite) (Fontana RJ 2009).¹⁸ The HERC will independently decide attribution and will communicate in writing with the sponsor. The results of the HERC review will be used in assessing the primary and secondary endpoints. The result of these analyses may be presented separately from the final clinical study report (CSR).

The Investigator must complete the liver dysfunction details eCRF and submit it within 24 hours of awareness through the SAE reporting pathway (described in [Section 7.3.8.3](#)) for any subject who develops an Adverse Event of Special Interest (AESI) related to abnormal liver chemistry test results or clinical signs or symptoms. Specifically, any subject who

- develops any signs or symptoms of hepatic dysfunction (see Appendix 4 [[Section 13.4](#)])
- discontinues treatment due to a liver-related AE,
- reports a serious liver-related AE,
- develops ALT or AST levels $>3 \times$ ULN,
- develops total bilirubin levels $>2 \times$ ULN.

The AESI report form should be updated as new information becomes available.

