8.4 Safety Analyses

8.4.1 Primary Hepatic Safety Endpoint

Descriptive statistics (n, percentage, 95% confidence interval) will be used to summarize the proportion of subjects who develop ALT levels $>3 \times \text{ULN}$ that were assessed by the independent HERC to be at least probably related to lixivaptan and resulted in discontinuation of the study drug during the Titration or Maintenance Periods.

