4 STUDY ENDPOINTS

4.1 **Primary Endpoint**

The primary endpoint is to assess the proportion of subjects who develop alanine aminotransferase (ALT) levels >3 x Upper Limit of Normal (ULN) during the Titration or Maintenance Periods that were assessed by the independent Hepatic Events Review Committee (HERC) to be at least probably related to lixivaptan and resulted in discontinuation of the study drug.

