8.6.2 Analysis of Secondary Safety Endpoint

Similarly, descriptive statistics (n and percentage) along with exact binomial 95% CI will be presented to summarize the following 2 secondary endpoints:

- The proportion of subjects who develop ALT levels >5 x ULN that were assessed by the independent HERC to be related to lixivaptan and resulted in discontinuation of the study drug during the Titration and Maintenance Periods.
- The proportion of subjects who develop ALT levels >3 x ULN that were assessed by the independent HERC to be related to lixivaptan and resulted in dose reduction of the study drug during the Titration and Maintenance Periods.

The above summaries will be presented additionally based on the investigator decision alone as documented in the CRF.

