8.6.5 Adverse Event (AE)

All AE verbatim descriptions will be coded using the MedDRA, version 23.0 or higher.

A TEAE is defined as any event not present before exposure to study drug or any event already present that worsens in either intensity or frequency after exposure to study drug. For this study, pregnancies and liver events are considered to be AESIs (Adverse Events of Special Interest). All AEs will be summarized by period (titration and maintenance period, follow-up period, and overall).

If a subject experiences multiple AEs under the same preferred term (system organ class), then the subject will be counted only once for that preferred term (system organ class). If a subject experiences the same AE more than once with different severity, then the event with the maximum severity will be tabulated in "by maximum severity" tables. In addition, AEs with a missing intensity will be presented in the summary table as an intensity category of "Missing."

If a subject, experiences the same AE more than once with different relationship, then the event with the strongest relationship will be tabulated in "by strongest relationship" tables. TEAEs with a missing relationship to study medication will be regarded as "Possible" to study medication. Adverse events with a relationship to study drug considered possibly, probably, or definitely related will be considered related.

An overview table will also be presented with the number and percentage of subjects as well as number of events for the following categories:

- At least one AE
- At least one TEAE
- At least one Serious TEAE
- Related TEAE
- Related Serious TEAE
- Any TE-AESI
- TEAEs by maximum severity
- TEAEs by strongest relationship to the study drug
- TEAEs leading to dose modifications (i.e. dose reduced or dose interrupted)
- TEAEs leading to study drug withdrawal
- TEAEs leading to death.

All TEAEs will be summarized as below:

- TEAEs by SOC and PT
- Serious TEAEs by SOC and PT
- Related TEAEs by SOC and PT
- TE-AESI by SOC and PT
- TEAEs leading to deaths by SOC and PT
- TEAEs leading to drug modification by SOC and PT
- TEAEs leading to study drug withdrawal by SOC and PT
- TEAEs by SOC, PT, and severity
- TEAEs by SOC, PT, and maximum severity
- TEAEs by SOC, PT, and relationship
- TEAEs by SOC, PT, and strongest relationship
- TEAEs by PT
- Serious TEAEs by PT
- Related TEAEs by PT

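### The primary endpoint counts HERC grades of probable or higher, but SAP 8.6.1 says only related and the synopsis analysis text says at least highly likely

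*SAP*

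**What the plan says.** The endpoint definitions agree with each other. SAP 4.1 counts ALT elevations above 3 x ULN judged by the HERC "to be at least probably related to lixivaptan and resulted in discontinuation of the study drug". Protocol 2.2.1 and the synopsis criteria for evaluation use the same cut-off, and Protocol 8.4.1 carries it into the analysis: "assessed by the independent HERC to be at least probably related to lixivaptan and resulted in discontinuation of the study drug".

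Two analysis texts depart from it. The statistical methods in the protocol synopsis describe the primary result as cases "assessed by the independent HERC to be at least highly likely related to lixivaptan". SAP 8.6.1 gives no grade and counts subjects who "develop ALT levels >3 x ULN that were assessed by the independent HERC to be related to lixivaptan and resulted in discontinuation".

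The two hepatic secondary endpoints show the same gap. Protocol 2.2.2 and 8.4.2 and SAP 4.2.1 define them with at least probably. The synopsis analysis text has only "assessed by the independent HERC to be related to lixivaptan and resulted in lixivaptan dose reduction", and SAP 8.6.2 has "assessed by the independent HERC to be related to lixivaptan and resulted in dose reduction of the study drug"; both also omit the grade for the 5 x ULN endpoint.

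The only SAP rule on what counts as related is in 8.6.5: "Adverse events with a relationship to study drug considered possibly, probably, or definitely related will be considered related". It is written for adverse events and does not mention HERC grades.

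**The concern.** The causality cut-off is part of the event definition, so it decides who is in the numerator of the primary endpoint and of both hepatic secondary endpoints. Someone programming from SAP 8.6.1 finds no cut-off there. Someone working from the synopsis analysis text finds one that excludes a grade the definition includes.

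Reading the bare word in SAP 8.6.1 as shorthand for SAP 4.1 is plausible, but no passage says so. There is also a competing reading in the same document. SAP 8.6.1 and 8.6.2 repeat each summary on the investigator's decision alone, and investigators grade adverse-event causality on the scale that the 8.6.5 rule collapses, with possibly counted as related. Carried over to HERC grades, that rule would add a further grade. The shorthand reading also cannot explain the synopsis, because highly likely is a separate named grade on the HERC scale.

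The study is open-label. A cut-off left to be inferred once the ratings are known invites a choice made with the results in view.

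**Working it through.** The plan has no figure to reproduce here. The sample size of up to 50 is taken from a similar study with another drug, and no event rate is assumed. The check is a comparison of passages, followed by an illustration of size.

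**Step 1. Cut-offs side by side.** Scores are those of Protocol Appendix 2 and SAP Appendix II (1 definite, 2 highly likely, 3 probable, 4 possible, 5 unlikely, 6 unrelated, 7 insufficient data).

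| Place | Cut-off | Scores counted |
|---|---|---|
| Primary: synopsis criteria, Protocol 2.2.1 and 8.4.1, SAP 4.1 | at least probably | 1 to 3 |
| Primary: synopsis statistical methods | at least highly likely | 1 to 2 |
| Primary: SAP 8.6.1 | related | not stated (1 to 4 only if the adverse-event rule were borrowed) |
| Hepatic secondary: synopsis criteria, Protocol 2.2.2 and 8.4.2, SAP 4.2.1 | at least probably | 1 to 3 |
| Hepatic secondary: synopsis statistical methods, SAP 8.6.2 | related | not stated |

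**Step 2. The percentage bounds behind the grades.** Protocol 7.3.7.3 uses "6 to 25% = unlikely, 25% to 50% = possibly, 51% to 75% = probably, 76% to 95% = very likely". The two appendices use 25-49 for possible, 50-74 for probable and 75-95 for highly likely.

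| Likelihood | Protocol 7.3.7.3 | Appendices |
|---|---|---|
| 25% | unlikely and possibly | possible |
| 50% | possibly | probable |
| 75% | probably | highly likely |

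Protocol 7.3.7.3 puts 25% in two categories. For an at-least-probably count, only a rating of exactly 50% changes sides, so this is a smaller point.

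**Step 3. Size, with assumed ratings.** A qualifying case is a subject with ALT above 3 x ULN during titration or maintenance that led to discontinuation. SAP 8.6.1 asks for exact binomial intervals, so for x events in n the limits are Beta⁻¹(0.025; x, n−x+1) and Beta⁻¹(0.975; x+1, n−x). For x = 0 the upper limit is 1 − 0.025^(1/n), which at n = 50 is 7.1%.

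(a) n = 50, with four qualifying cases rated definite, highly likely, probable and possible:

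| Reading | Events | Exact 95% CI |
|---|---|---|
| At least highly likely | 2/50 = 4.0% | 0.5 to 13.7% |
| At least probably | 3/50 = 6.0% | 1.3 to 16.5% |
| Related, if possible is included | 4/50 = 8.0% | 2.2 to 19.2% |

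(b) n = 50, with one qualifying case rated probable: 0/50 (0 to 7.1%) under the synopsis analysis text, and 1/50 = 2.0% (0.1 to 10.6%) under the definition.

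(c) The same single case at n = 6: 0/6 against 1/6 = 16.7%. The denominator is an assumption, because SAP 9 gives only the number entering maintenance. Only counts matter here, since SAP 9 plans no statistical analyses.

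With no qualifying case, every reading gives zero.

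**The case against.** The strongest reply is that the intended cut-off can be worked out. Every endpoint definition and Protocol 8.4.1 agree on it. SAP 8.6.1 and 8.6.2 are headed as analyses of endpoints that SAP section 4 defines. Protocol 8.7 says a major change to the primary analysis would also appear in a protocol amendment; Protocol Version 4, issued after the Version 3 on which the SAP is based, keeps the cut-off in 8.4.1. SAP 9 lists no change to it. All of this stands, and it makes the correction easy to choose. It does not remove the contradictory sentence in the synopsis or put a cut-off into the SAP analysis sections.

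The second reply is that the study was stopped with 6 subjects in maintenance and no statistical analyses will be run, so the 50-subject intervals will never be reported. That lowers the practical weight, and the documents report no qualifying case. But Table 14.3.2.1 and Listing 16.2.7.2 in SAP Appendix IV are still to be produced for these endpoints, and a count needs one rule.

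Two smaller objections also have force. The 4/50 row depends on borrowing a rule written for adverse events, so it is a conditional case and no more. The percentage bounds matter only at exactly 50%.

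**Conclusion.** The inconsistency is real, and the text is wrong as written, because one analysis text contradicts the definition and another leaves the cut-off out. Following the synopsis analysis text would drop any case rated probable. One such case is the difference between 0/50 with an upper limit of 7.1% and 1/50 = 2.0% with an upper limit of 10.6%. These figures assume full enrolment and hypothetical ratings. In the terminated study the effect is on counts only, and there is none if no subject qualifies. It must still be corrected, because it concerns the primary endpoint and the outputs that report it remain planned.

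**What to change.** In SAP 8.6.1, SAP 8.6.2 and the statistical methods of the synopsis, replace the present wording with the cut-off the sponsor already defined: at least probably related (DILIN score 1, 2 or 3). Table 14.3.2.1 and Listing 16.2.7.2 should then use that one definition. A separate row for score 7 (insufficient data) would be useful but is optional.

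Use one non-overlapping set of percentage bounds for the HERC in Protocol 7.3.7.3, Protocol Appendix 2 and SAP Appendix II. Protocol 4.2.7 and 7.3.7.2 also use the 50% boundary, with different wording, for restarting study drug. The sponsor must reconcile those passages separately, and no rule is proposed here.

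The work is a change of wording in two SAP sections and the synopsis, plus one aligned percentage table, with no new data. The protocol edits would go through an amendment under Protocol 11.2.1. The SAP wording is what the remaining table and listing depend on most directly, so it should be corrected first.

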8.6.2 Analysis of Secondary Safety Endpoint

Similarly, descriptive statistics (n and percentage) along with exact binomial 95% CI will be presented to summarize the following 2 secondary endpoints:

- The proportion of subjects who develop ALT levels >5 x ULN that were assessed by the independent HERC to be related to lixivaptan and resulted in discontinuation of the study drug during the Titration and Maintenance Periods.
- The proportion of subjects who develop ALT levels >3 x ULN that were assessed by the independent HERC to be related to lixivaptan and resulted in dose reduction of the study drug during the Titration and Maintenance Periods.

The above summaries will be presented additionally based on the investigator decision alone as documented in the CRF.

8.6.3 Analysis of Additional Hepatic Safety Endpoints

The proportion of subjects along with the exact binomial 95% CI who develop the following abnormalities during the Titration and Maintenance Periods will be tabulated and presented descriptively:

- >3 x, 5 x, >10 x, and 20 x ULN elevations for ALT
- >3 x, 5 x, 10 x, and 20 x ULN elevations for Aspartate aminotransferase (AST)
- >3 x, 5 x, 10 x, and 20 x ULN elevations for either ALT or AST
- ALT or AST levels >2 x their baseline
- Any elevation of total bilirubin (TBL) $>2 \times ULN$
- Any elevation of alkaline phosphatase (ALP) >2 x ULN
- Elevation of aminotransferase (>3 x ULN) accompanied by elevated bilirubin (>2 x ULN) will be evaluated using Drug-Induced Serious Hepatotoxicity (eDISH) plots
- Elevation of aminotransferase in temporal association with nausea, vomiting, anorexia, abdominal pain, or fatigue will be explored graphically using swimmer plots.
- Possible liver-related deaths and liver-related treatment discontinuations.

The liver dysfunction occurring during the titration and maintenance period judged using the Drug Induced Liver Injury Network (DILIN) (Appendix II) probability criteria independently by investigator and HERC will be listed separately.

8.6.4 Analysis of Additional Potential Hepatic Safety Endpoints

The summary of additional hepatic safety assessments will be presented based on potential hepatic testing (Appendix III) based on liver chemistry abnormalities. The assessments will be

presented tabulated using descriptive statistics or frequency and percentages based on the data type. These data will further be listed separately based on all subjects.

8.6.5 Adverse Event (AE)

All AE verbatim descriptions will be coded using the MedDRA, version 23.0 or higher.

A TEAE is defined as any event not present before exposure to study drug or any event already present that worsens in either intensity or frequency after exposure to study drug. For this study, pregnancies and liver events are considered to be AESIs (Adverse Events of Special Interest). All AEs will be summarized by period (titration and maintenance period, follow-up period, and overall).

If a subject experiences multiple AEs under the same preferred term (system organ class), then the subject will be counted only once for that preferred term (system organ class). If a subject experiences the same AE more than once with different severity, then the event with the maximum severity will be tabulated in "by maximum severity" tables. In addition, AEs with a missing intensity will be presented in the summary table as an intensity category of "Missing."

If a subject, experiences the same AE more than once with different relationship, then the event with the strongest relationship will be tabulated in "by strongest relationship" tables. TEAEs with a missing relationship to study medication will be regarded as "Possible" to study medication. Adverse events with a relationship to study drug considered possibly, probably, or definitely related will be considered related.

An overview table will also be presented with the number and percentage of subjects as well as number of events for the following categories:

- At least one AE
- At least one TEAE
- At least one Serious TEAE
- Related TEAE
- Related Serious TEAE
- Any TE-AESI
- TEAEs by maximum severity
- TEAEs by strongest relationship to the study drug
- TEAEs leading to dose modifications (i.e. dose reduced or dose interrupted)
- TEAEs leading to study drug withdrawal
- TEAEs leading to death.

All TEAEs will be summarized as below:

- TEAEs by SOC and PT
- Serious TEAEs by SOC and PT
- Related TEAEs by SOC and PT
- TE-AESI by SOC and PT
- TEAEs leading to deaths by SOC and PT
- TEAEs leading to drug modification by SOC and PT
- TEAEs leading to study drug withdrawal by SOC and PT
- TEAEs by SOC, PT, and severity
- TEAEs by SOC, PT, and maximum severity
- TEAEs by SOC, PT, and relationship
- TEAEs by SOC, PT, and strongest relationship
- TEAEs by PT
- Serious TEAEs by PT
- Related TEAEs by PT

Adverse events will be presented in data listings including dose level, subject number, start/end dates/times of event, MedDRA system organ class, preferred term, duration of the event, seriousness, severity, action taken, relationship to study drug and outcome.

The following by subject listings will be provided for all subjects:

- AEs
- Serious AEs
- TE-AESIs
- AEs leading to Deaths
- AEs leading to dose modification (including interruption, reduction and discontinuation)

